### 5.2.2. LY2875358

LY2875358 is a humanized immunoglobulin G, subclass 4 bivalent mAb that can block signaling of the HGF/MET pathway via 2 modes of action. LY2875358 blocks ligand-dependent and ligand-independent MET signaling as demonstrated in preclinical studies described in the IB. Ligand-dependent activation of the MET pathway is impaired upon binding of LY2875358 to MET by limiting HGF interaction with the receptor. In addition, binding of LY2875358 to MET causes receptor internalization and degradation of MET resulting in suppression of ligand-independent activation of MET.

LY2875358 has been evaluated in the first-in-human Phase 1 Study I4C-MC-JTBA (JTBA) and the Phase 1 Study I4C-JE-JTBD (JTBD) in Japanese patients, with the primary objective being to determine a recommended Phase 2 dose (RP2D) range of LY2875358 as monotherapy and in combination with erlotinib. In both studies, LY2875358 was administered intravenously (IV) Q2W using a flat dosing scheme at doses of up to 2000 mg as monotherapy and in combination with erlotinib. As of 18 March 2014, cumulatively 184 subjects have received LY2875358 in the 6 ongoing clinical trials, including 123 patients receiving LY2875358 monotherapy. No dose-limiting toxicities (DLTs) have been reported for either LY2875358 monotherapy or for combination therapy with erlotinib in the dose escalation Studies JTBA and JTBD. The most frequently reported treatment-emergent adverse events (TEAEs) possibly related to LY2875358 monotherapy across all studies within the LY2875358 clinical program include fatigue (16.3%), nausea (9.8%), diarrhea (5.7%), and peripheral edema (5.7%). A total of 7 possibly related TEAEs ( $\geq$ Grade 3) for LY2875358 monotherapy were reported: 2 events of fatigue and 1 event

each of peripheral edema, pancreatitis, anemia, nausea, and hyponatremia. A total of 87 SAEs have been reported in the Lilly Safety System (LSS) database in Studies JTBA and JTBD as of 18 March 2014. Of these SAEs, 5 were considered possibly related to LY2875358 by either the investigator or the sponsor, including 1 event each of thrombocytopenia, pancreatitis, dyspnea, pyrexia, and peripheral edema in a patient with pre-existing edema.

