5.2. Determination of Sample Size

To determine a recommended schedule and dose range of LY2875358 in combination with ramucirumab that may be safely administered to patients with advanced and/or metastatic cancer, an adequate patient sample size is required. A sufficient sample size will allow for an accurate evaluation of the relationship between exposure and toxicity, as well as an evaluation of the relationship between exposure and pharmacological effects using descriptive statistics and appropriate modeling techniques, if data warrant. This sample size is estimated to be a total of approximately 70 patients (6-12 [Part A] + 60 [Part B]).

For Part A, following a 3+3 dose escalation scheme, the sample size calculation assumes that cohorts will include 3 to 6 patients. If 2 cohorts for the intended 2 dose levels for LY2875358 (i.e., 750 and 2000 mg) are needed to determine a recommended dose range for LY2875358 in combination with ramucirumab, then approximately 6-12 patients will be enrolled in Part A. To ensure accurate evaluation of safety, tolerability, or PK/PD biomarkers, additional patients may be enrolled during Part A if deemed appropriate based on agreement between the investigators and the sponsor.

For Part B, the sample size of approximately 15 patients per expansion cohort was selected to allow adequate confirmation of safety and tolerability of LY2875358 in combination with ramucirumab and to identify evidence of preliminary clinical activity worthy of further investigation in Phase 2, analogous to the first stage of a Simon 2-stage design. If the true clinical RR according to RECIST for the combination of ramucirumab and LY2875358 in 1 of the tumor types selected is 10%, then there is a 79% chance of observing at least 1 patient with a clinical response, which might warrant further study of the regimen. On the other hand, if the true RR is close to the RR of ramucirumab monotherapy (for example, 3% in the REGARD trial, Table JTBF.5.2), then there is a 36.7% chance of incorrectly concluding that the regimen merits further study. Table JTBF.5.1 demonstrates chance of observing at least 1 patient with clinical response for the combination of ramucirumab and LY2875358. For instance, if the true clinical RR is 10% across all four expansion cohorts in part B, there is 49.3% probability of observing

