6.1. General Considerations

Statistical analysis of this study will be the responsibility of Lilly. The interpretation of the study results will be the responsibility of the investigator with the Lilly Clinical Research Physician (CRP), pharmacokineticist, statistician and clinical development associate. The Lilly CRP and statistician will also be responsible for the appropriate conduct of an internal review process for both the final study report and any study-related material to be authorized for publication by Lilly.

The analyses for this study will be descriptive, except for possible exploratory analyses as deemed appropriate. Data analyses will be provided by dose levels and for all patients combined wherever appropriate. For continuous variables, summary statistics will include number of patients (N), mean, median, standard deviation (SD), standard error (SE), minimum, and maximum. Categorical endpoints will be summarized using N, frequency, percentages, and associated SE.

Exploratory analyses of the data that are not described in the protocol will be conducted as deemed appropriate.

In Part A, all data will be summarized by cohort (and all patients combined when appropriate), unless stated otherwise. In Part B, all data will be summarized by tumor-specific cohort.

Any change to the data analysis methods described in the protocol will require an amendment ONLY if it changes a principal feature of the protocol. Any other change to the data analysis methods described in the protocol and the justification for making the change will be described in the clinical study report.

Table JTBF.6.1. explains the data handling conventions and rules used in the analysis:

Table JTBF.6.1. Data Handling Conventions and Rules

Term	Definition or Rule
Study Day	If assessment is on or after date of first dose then (date of assessment) – (date of first study drug dose) +1
	If assessment precedes first dose of drug then (date of assessment) – (date of first study drug dose)
	There is no study day 0. Study day 1 is the date of first dose and study day -1 is the day before the first dose.
Cycle Day	If assessment is on or after date of first dose in the cycle then (date of assessment) – (date of first study drug dose in cycle) +1
	If assessment precedes first dose of drug in a cycle then (date of assessment) – (date of first study drug dose in cycle)
	There is no cycle day 0. Cycle day 1 is the date of first dose in the

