6.11. Safety Analyses

All patients who receive at least 1 dose of ramucirumab and/or LY2875358 will be evaluated for safety and toxicity. Adverse event terms and severity grades will be assigned by the investigator using NCI CTCAE Version 4.03.

Safety analyses will include summaries of the following:

- AEs, including severity and possible relationship to study drugs
- Dose delays and dose adjustments

- Laboratory values
- Vital signs
- DLTs at each dose level
- ECG readings
- Deaths on treatment and within 30 days of treatment discontinuation

Hospitalizations and transfusions during the study treatment period or during the 30-day postdiscontinuation follow-up period will be summarized by study parts.

Dose Limiting Toxicity and Equivalent Toxicity

an AE during Cycle 1 that is possibly, probably, or definitely related to treatment with LY2875358 in combination with a fixed regimen of ramucirumab and fulfills any 1 of the following criterion using the NCI CTCAE Version 4.03:

- \geq Grade 3 non-hematological toxicity. Exceptions will be made for:
 - nausea, vomiting, diarrhea, constipation, or skin rash that persists for ≤ 3 days following appropriate supportive care intervention
 - Grade 3 hypertension in which systolic BP ≥ 160 mmHg and/or diastolic BP ≥ 100 mmHg persist < 7 days after intensified antihypertensive therapy is initiated
- Grade 4 hematological toxicity of ≥ 7 days duration
- \geq Grade 3 thrombocytopenia with \geq Grade 2 bleeding
- Any febrile neutropenia
- Any other significant toxicity deemed by the primary investigator and Lilly clinical research personnel to be dose-limiting (eg, any toxicity that is possibly related to the study medication that requires the withdrawal of the patient from the study during Cycle 1).

Infusion-related reactions (including hypersensitivity reactions and anaphylaxis) should not be considered as DLTs unless the investigator or Lilly medical monitor provides compelling rationale to support their inclusion as a DLT.

Patients in Part A (Cycle 2 or greater) and Part B will be evaluated on an ongoing basis for AEs. In these patients, a DLT-equivalent toxicity will be defined based on trends of any clinical significant toxicity deemed by the study investigators and Lilly clinical research personnel to be dose-limiting and related to study drug(s)s. The investigators and Lilly CRP/CRS will have to agree as to whether such AEs are considered as DLT-equivalent.

Maximum Tolerated Dose

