6.11.2. Adverse Events

Common Terminology Criteria for Adverse Events (CTCAE) v 4.0 will be used to report AEs. Any minor version of CTCAE Version 4.0 (for example, CTCAE Version 4.03) may be used for this study. Minor updates to the CTCAE Version 4.0 from the NCI will not necessitate a protocol amendment, and the use of an updated CTCAE Version 4.0 will not be considered a protocol violation. For AEs without matching terminology within the NCI-CTCAE v 4.0 criteria, the investigator will be responsible for selecting the appropriate system organ class and assessing severity grade based on the intensity of the event. The verbatim text for these AEs will be coded according to the available version of the Medical Dictionary for Regulatory Activities (MedDRA). For analysis and reporting of AEs, the MedDRA coded terms corresponding to these CTCAE “other-specify” AEs will be used.

A treatment-emergent adverse event (TEAE) is defined as (i) adverse event that occurred after the administration of at least one dose of study therapy, regardless of causality; or (ii) adverse events already present during screening that worsen following exposure to the treatment,

regardless of causality. Event worsen in severity is supported by higher CTCAE grade observed after first dose of study treatment for the corresponding MedDRA lower level term.

The CTCAE term (or MedDRA Lower Level Term (LLT) for cases of CTCAE “other-specify”) will be used in the treatment-emergent determination.

The number of patients who experienced a TEAE, SAE, TEAE related to study drug, died, or discontinued from the study due to an AE will be summarized by treatment. Treatment-emergent adverse events will be summarized by System Organ Class (SOC), by decreasing frequency within SOC, and by maximum CTCAE severity grade, including the total of patients with maximum severity grade ≥ 3 .

Historical illnesses (coded according to the MedDRA dictionary) and pre-existing conditions (using CTCAE terms and severity grades) will be listed by part and by cohort. Historical illnesses are events in the past that ended before the Screening Visit. Pre-existing conditions are events that are present at screening and continue. The pre-existing conditions will be presented by patient and can be combined with the adverse event listing, so that the history of the pre-existing conditions/adverse events can be traced.

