6.12. Efficacy Analyses

As a coprimary objective for Part B, this study will evaluate preliminary antitumor activity observed with ramucirumab in combination with LY2875358 in the tumor-specific expansion cohorts.

Overall Response Rate (ORR): ORR is defined as the proportion of patients who exhibit a confirmed CR or PR relative to baseline as defined by RECIST 1.1 (Eisenhauer et al. 2009).

ORR is computed as the number of responders divided by the total number of treated patients. A responder is defined as any patient who exhibits a confirmed CR or PR relative to baseline

assessment, done on or up to 7 days prior to Cycle 1 Day 1. Patients with response that is deemed not evaluable will be considered non-responders and will be included in the denominator for the purpose of calculating ORR. ORR will be assessed within each cohort, ORR with 95% CIs will be estimated using the Clopper-Pearson method.

Progression-Free Survival (PFS): The PFS time is measured from the date of receiving the first dose of study drug to the date of first objective progression as assessed by the investigator or the date of death due to any cause, whichever is earlier. Table 6.2 provides additional details. The censoring is taken in the following order:

- If a patient does not have a complete baseline disease assessment, then the PFS time will be censored at the enrollment date, regardless of whether or not objectively determined disease progression or death has been observed for the patient; otherwise,
- If a patient is not known to have died or have objective progression as of the data inclusion cutoff date for the analysis, the PFS time will be censored at the last evaluable objective progression-free disease assessment date.

If a patient has a missed visit prior to an event (progression or death), then the PFS time will be censored at the last evaluable assessment prior to the event.

Table 6.2. Definition of PFS

Situation	Outcome	Date of Progression or Censoring
Death before first objective PD assessment	Progressed	Date of death
Objective PD	Progressed	Date of first radiologic assessment showing progressive disease
No evaluable baseline tumor assessments	Censored	Enrollment date
No progression	Censored	Date of last radiologic assessment of measured lesions showing no progression
New systemic anticancer treatment started	Censored	Date of last radiologic assessment of measured lesions showing no progression prior to the commencement of new systemic anticancer treatment

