Death or progression after more than one missed visit (after 3 months since last assessment)	Censored	Date of last radiologic assessment of measured lesions showing no progression prior to the missed visit

The date of first documented objective disease progression must be recorded on the CRF even if it occurs after the patient has started a new therapy.

Disease Control Rate (DCR): The proportion of patients in the analysis population who exhibit an SD or confirmed CR or PR relative to baseline during the study. Response is defined by RECIST 1.1 (Eisenhauer et al. 2009).

Change in Tumor Size (CTS): The change in tumor size from baseline to the measurement with the smallest tumor size during the study period. Change in tumor size will be assessed in each patient using radiographic imaging. The tumor size of target lesions will be determined as defined by RECIST 1.1 (Eisenhauer et al. 2009).

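### Outside ORR the only planned precision measure for categorical endpoints is a standard error, which is 0 at zero events; DLT and adverse-event rates need an exact interval, and DCR should have the one ORR gets

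*SAP*

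**What the plan says.** SAP 6.1 sets a default for everything categorical: "Categorical endpoints will be summarized using N, frequency, percentages, and associated SE". Protocol 12.1 has the same sentence. The one departure is in SAP 6.12: "ORR with 95% CIs will be estimated using the Clopper-Pearson method", within each cohort.

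The other proportions have no such provision:

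- DCR, also in SAP 6.12, is defined as "The proportion of patients in the analysis population who exhibit an SD or confirmed CR or PR relative to baseline during the study", with no interval.
- SAP 6.11 lists "DLTs at each dose level" among the safety summaries.
- SAP 6.11.2 summarizes "The number of patients who experienced a TEAE, SAE, TEAE related to study drug, died, or discontinued from the study due to an AE".

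None of these names a measure of precision, so the SAP 6.1 default applies.

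The denominators are small. For Part A, SAP 5.2 says that "the sample size calculation assumes that cohorts will include 3 to 6 patients". For Part B it refers to "the sample size of approximately 15 patients per expansion cohort". On earlier experience, Protocol 5.2.2 says of the dose-escalation studies: "No dose-limiting toxicities (DLTs) have been reported for either LY2875358 monotherapy or for combination therapy with erlotinib".

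**The concern.** The estimated SE of a percentage depends on the observed percentage and collapses to 0 when nobody has the event, however few patients were observed. At one event in a small group it is positive, but it does not convey how skewed the uncertainty is. The primary objective is a schedule and dose range that can be given safely, and the safety profile is a secondary objective. A table entry of 0% with SE 0 tells a reader nothing about how high a toxicity rate remains compatible with the data. The SAP already specifies a suitable method for ORR and does not extend it to these rates.

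DCR raises a different and smaller point. It is reported beside ORR, in the same patients, yet only ORR gets an interval. Protocol 5.2.1.3 cites the earlier renal-cell DCR with one (64.1%; 95% CI 47.2% to 78.8%), so this study's figure would be read against a result reported more fully.

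**Working it through.** **Plan's own binomial figures.** SAP 5.2 gives the chance of at least one responder in 15 as 79% at a true rate of 10% and 36.7% at 3%. With 1 − (1 − p)^15, these are 1 − 0.90^15 = 79.4% and 1 − 0.97^15 = 36.7%. Both reproduce, and the same model is used below.

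**Formulas.**

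- SE = sqrt(p(1 − p)/n), with p the observed proportion. This is an assumption, because the SAP states no formula.
- Exact 95% limits are two-sided Clopper-Pearson. At zero events the lower limit is 0 and the upper limit is 1 − 0.025^(1/n).

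| Result | SE (points) | Exact 95% interval |
|---|---|---|
| 0/3 | 0 | 0 to 70.8% |
| 0/6 | 0 | 0 to 45.9% |
| 0/15 | 0 | 0 to 21.8% |
| 1/6 | 15.2 | 0.4% to 64.1% |
| 7/15 | 12.9 | 21.3% to 73.4% |

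For 1/6, SE = sqrt(0.1667 × 0.8333/6) = 15.2 points. A reader who forms 16.7% ± 1.96 × 15.2 gets about −13% to 46%. The lower end is impossible and the upper end is well short of 64%.

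**How often a zero count would occur.** The documents give no expected DLT rate for the combination, so 5% and 10% are assumed as illustrations. P(0) = (1 − p)^n.

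| n | p = 5% | p = 10% | Zero is the likeliest count if p is below 1/(n + 1) |
|---|---|---|---|
| 3 | 85.7% | 72.9% | 25% |
| 6 | 73.5% | 53.1% | 14.3% |
| 15 | 46.3% | 20.6% | 6.25% |

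The row for 6 treats six patients as a fixed number. Under the 3+3 rule a level without a DLT normally stays at three. It reaches six without a DLT only if extra patients are admitted (Protocol 8.1.1 and 9.3). The commoner zero case is therefore 0/3, which has the widest exact interval.

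**Adverse events in 15 patients.** At the monotherapy rates in Protocol 5.2.2:

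- 5.7% (diarrhea, peripheral edema): P(0/15) = 0.943^15 = 41.5%; likeliest count 0.
- 9.8% (nausea): 0.902^15 = 21.3%; likeliest count 1.
- 16.3% (fatigue): 0.837^15 = 6.9%; likeliest count 2.

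**DCR in 15 patients.** SAP Table JTBF.5.3 lists 49% (gastric) and 64% (renal cell):

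- P(0/15) = 0.51^15, about 4 in 100,000, and 0.36^15, about 2 in 10 million.
- At 7/15, the likeliest count at 49%, 46.7% ± 1.96 × 12.9 gives about 21% to 72%, close to the exact 21.3% to 73.4%.

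For DCR the SE is therefore usable at the likely counts. What is missing is the interval itself.

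**The case against.** The strongest reply is that nothing is decided on the SE. Escalation and the MTD follow a count rule: one DLT leads to up to three more patients, and two or more of six stops escalation (Protocol 9.2.2.3; SAP 6.11). Part B de-escalation rests on agreed DLT-equivalent toxicities (Protocol 9.2.2.2 and 9.2.3.3). This stands. A reader might infer that dose selection rests on faulty error bars, but the documents do not support that.

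Second, N and frequency are printed in the same row, so a reader sees 0 of 3, and the analyses are declared descriptive with no normal interval planned. This also stands. The result is not literally presented as certain, and the −13% to 46% range is a reader's construction. But the one precision figure in the row is still 0.

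Third, a reader might infer that zero is the likeliest result for every rate reported this way. It is not. The calculations rule that out for disease control, and for the commoner adverse events in cohorts of 15.

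Fourth, the history without DLTs covers LY2875358 alone and with erlotinib, not with ramucirumab. Protocol 5.2.1.2 reports treatment-related hypertension of grade 3 or higher in 14% of hepatocellular patients on ramucirumab alone, although Protocol 9.2.2.2 exempts short-lived grade 3 hypertension from the DLT definition. This stands too, and is why the DLT probabilities are shown as a range.

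Finally, the sponsor could add intervals at reporting, since SAP 6.1 lets lesser changes of method be described in the study report. That is true, but nothing commits the sponsor to do so.

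**Conclusion.** The point holds as one about reported precision. For categorical endpoints other than ORR, the SE is the only planned measure, and it carries no information at zero events. In groups of 3, 6 and 15 it would be printed as 0 where the exact 95% upper limits are 71%, 46% and 22%. At 1/6 it is 15 points, against an exact interval of 0.4% to 64%. These situations are common for DLTs and uncommon adverse events if true rates are low.

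This rests on the usual SE formula and on assumed event rates of 5% to 10%. Clopper-Pearson also treats the number of patients as fixed, whereas 3+3 lets the data influence it, so limits at a dose level should be read as descriptive.

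For DCR the conclusion is only that it should have the interval ORR has. Sample size, escalation and dose selection are unaffected.

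**What to change.** In SAP 6.1 and Protocol 12.1, replace the SE for categorical endpoints, or accompany it, with the exact 95% Clopper-Pearson interval already specified for ORR. Name the rates it applies to, each with its denominator:

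- DLT rate by dose level
- TEAE, grade 3 or higher TEAE and SAE rates by cohort
- DCR by cohort, beside ORR

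Naming the rates avoids leaving an undefined set of key events to be chosen later. The cost is a sentence in each document and a small table-shell change. By SAP 6.1's own test, a change of analysis method forces a protocol amendment only if it alters a principal feature. This does not appear to, so the Protocol 12.1 wording could be aligned at the next amendment and the change noted in the study report. The drawback is that the intervals will look wide, which is what groups of this size support.

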6.2. Adjustments for Covariates

Adjustment for covariates is not applicable. However, the following variable are of interest and analysis with respect to these variables will be discussed in section 6.14 Subgroup Analyses:

- Age (≤ 65 years vs. > 65 years)
- Sex (male vs. female)
- Tumor types (Part B1: Gastric or GEJ adenocarcinoma; Part B2: Hepatocellular cancer (HCC); Part B3: Renal cell carcinoma (RCC, any histology); Part B4: Non-small cell lung cancer (NSCLC, squamous or non-squamous))
- ECOG performance status (0, 1 vs 2 in part A and 0 vs 1 in part B)

